## 3.2 Subject Selection

### 3.2.1 Recruitment and Informed Consent

Subjects will be recruited from high schools or communities in the Worcester region, and potentially elsewhere with similar TB epidemiology, through liaison with Education Department officials, teachers, parent organizations, and community organizations. Various methods of

recruitment may be used, such as classroom information sessions, advertising, referrals, word-of-mouth, or solicitation through subjects previously known to the clinical site. All recruitment materials will be approved by the Institutional Review Board (IRB) or Independent Ethics Committee (IEC). Interested subjects will be invited to participate in the informed consent and assent process. Informed consent will be obtained by the use of a written consent form approved by the IRB or IEC and signed and dated by the parent/legal guardian at the time of consent. Similarly, informed assent will be obtained by the use of a written assent form approved by the IRB or IEC and signed and dated by the subject at the time of assent. Potential subjects will be interviewed to ensure that they meet all entry criteria relating to history. The clinical investigator or designee will conduct the consent and assent discussions on an individual basis with each subject and parent/legal guardian and will allow adequate time for all questions to be addressed. Written informed consent and assent will be obtained prior to conducting any study-related procedures. A copy of the signed consent and assent forms shall be given to the subject and parent/legal guardian prior to conducting any study-related procedures.

Subjects who converted to a positive QFT-GIT at Month 6 or 12 will be approached for an additional QFT-GIT test, blood collection for absolute blood count and RNA, and evaluation for signs/symptoms of TB to be conducted at least 24 months after their initial vaccination. Informed consent will be obtained by the use of a written supplemental consent form approved by the IRB or IEC, and signed and dated by subject or by the subject's parent/legal guardian if subject is less than 18 years of age. Similarly, informed assent will be obtained by the use of a written assent form approved by the IRB or IEC, and signed and dated by the subject if the subject is less than 18 years of age.

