    - Participants who never converted or converted with reversion. Percentages (%) will be calculated based on the number of participants who did not have two missing QFT-GIT values within 6 months of post-initial conversion.

---

Document: Aeras\_C-040-404\_SAP\_V2\_0

Author: [name]

Version Number:

2.0

Version Date:

29SEP2017

Template No: CS\_TP\_BS016 – Revision 3

Reference: CS\_WI\_BS005

Effective Date: 01May2012

Copyright © 2012 Quintiles Transnational Corp. All rights reserved.

The contents of this document are confidential and proprietary to Quintiles Transnational Corp. Unauthorized use, disclosure or reproduction is strictly prohibited.

- Participants who never converted or converted with reversion and have non-positive (i.e., negative or missing) six-month post-initial-conversion QFT-GIT values. Percentages (%) will be calculated based on the number of participants who did not have two missing QFT-GIT values within 6 months of post-initial conversion.
      - Participants who never converted or converted with reversion and have non-positive (i.e., negative or missing) end of study QFT-GIT values. Percentages (%) will be calculated based on the number of participants who did not have the following combination of QFT-GIT values: +/m/m, +/+m/m or +/m/m/m where + = positive and m = missing.
    - o Comparisons of proportions between treatment groups for each category will be performed based on the Pearson chi-square test.
    - o Vaccine efficacy presented:
      - Point estimate (based on the conditional binomial Clopper-Pearson method with mid-p correction).
      - 95% CI (based on the conditional binomial Clopper-Pearson method with mid-p correction).
  - QFT-GIT end of study sustained conversion rates:
    - o Number and percentage (%) of participants in each conversion status category:
      - Yes.
      - No.
      - Missing.
    - o Hazard ratio (H4:IC31/comparator) presented:
      - Point estimates (based on the Cox regression model).
      - P-values for the comparison of the estimated hazard ratios of QFT-GIT end of study sustained conversion based on a one-sided log-rank test.
        - H4:IC31 versus Placebo.
        - BCG versus Placebo.
        - H4:IC31 versus BCG (at the request of the sponsor's partner).
    - o Vaccine efficacy presented:
      - Point estimate (based on the hazard ratio estimate).
      - 80% two-sided CI based on the hazard ratio estimate from the Cox regression model.

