### 14.3.3. DERIVATIONS

Based on the aforementioned, the following variables, as presented in the planned TLF shells, will be derived for post-vaccination visits and/or time points:

- QFT-GIT result classification (refer to Section 14.1.3: Derivations). Substitute the primary analysis threshold value with the alternative threshold value.
- Available follow-up time (months) until QFT-GIT:
  - o Months represent the available follow-up time (months) per participant since first QFT-GIT conversion.

---

Document: Aeras\_C-040-404\_SAP\_V2\_0

Author: [name]

Version Number:

2.0

Version Date:

29SEP2017

Template No: CS\_TP\_BS016 – Revision 3

Reference: CS\_WI\_BS005

Effective Date: 01May2012

Copyright © 2012 Quintiles Transnational Corp. All rights reserved.

The contents of this document are confidential and proprietary to Quintiles Transnational Corp. Unauthorized use, disclosure or reproduction is strictly prohibited.

- Negative at Month 24:
  - o Participants who are negative at Month 24 or who initially converted at Month 6 or Month 12 and are negative at the  $\geq 24$  Month call-back visit.
- Prevention of conversion OR conversion with reversion:
  - o Participants who are consistently negative OR
  - o Participants who have a negative QFT-GIT value within six months after their initial conversion (i.e., +/-/-, +/+/-, +/-/+, +/m/-, +/-/m).
- Prevention of conversion OR conversion with reversion and non-positive (i.e. negative or missing) QFT-GIT results at six-months post-initial-conversion:
  - o Participants who are consistently negative OR
  - o Participants who have a negative QFT-GIT value at the last available testing timepoint within six months after their initial conversion (i.e., +/-/-, +/+/-, +/m/-, +/-/m).
- Prevention of conversion OR conversion with reversion and non-positive (i.e., negative or missing) QFT-GIT results at the end of the study:
  - o Participants who are consistently negative throughout the study OR
  - o Participants who initially converted at Month 18 or Month 24 (i.e., +/-/-, +/+/-, +/m/-, +/-/m) and later reverted OR
  - o Participants who initially converted at Month 6 or Month 12 and have a call-back Month 24 visit that is negative (i.e., +/-/-/-, +/+/-/-, +/+/+/-, +/-/+/-, +/-/m/-, +/m/-/-, +/m/m/-, +/+/m/-).
- QFT-GIT end of study sustained conversion status:

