  - o Yes: At 3 and 6 months following first QFT-GIT conversion AND at the Month 24 call-back visit (if applicable), QFT-GIT result classifications are derived as positive.
  - o No: At 3 and/or 6 months following first QFT-GIT conversion and/or at the Month 24 call-back visit (if applicable), QFT-GIT result classification is derived as negative.
  - o Missing: None of the aforementioned QFT-GIT result classifications (yes, no) has been assigned at 3 or 6 months post-conversion or at the Month 24 call-back visit, QFT-GIT result classification is derived as missing.
- The confidence interval for VE is calculated using the conditional binomial method (Clopper-Pearson method with mid-p correction) as follows:  
 The number of participants with a conversion ( $n_A$ ) in one of the treatment groups (for example H4:IC31) and the number ( $n_B$ ) of participants with a conversion in another treatment group (for example Placebo), are assumed to have Independent Poisson distributions with rate parameters  $\lambda_A$  and  $\lambda_B$ , respectively, but inference is conditional on the total number of conversions,  $n = n_A + n_B$ . Conditional on  $n$ ,  $n_A$  has a Binomial distribution,  $\text{Bin}(n, \pi)$ , where

$$\pi = \frac{\lambda_A F_A}{\lambda_A F_A + \lambda_B F_B} = \frac{\theta F_A}{\theta F_A + F_B}$$

$\theta = \lambda_A \lambda_B$  and  $F_A$  and  $F_B$  are the total lengths of follow-up across all subjects in the relevant treatment groups (Treatment Group A/Treatment Group B), that is,  $F = \sum (\text{Duration of VE Follow-up Period [Days]})$ .

Document: Aeras\_C-040-404\_SAP\_V2\_0

Author: [name]

Version Number:

2.0

Version Date:

29SEP2017

Template No: CS\_TP\_BS016 – Revision 3

Reference: CS\_WI\_BS005

Effective Date: 01May2012

Copyright © 2012 Quintiles Transnational Corp. All rights reserved.

The contents of this document are confidential and proprietary to Quintiles Transnational Corp. Unauthorized use, disclosure or reproduction is strictly prohibited.

A point estimate and exact two-sides 95% CI ( $\pi_L, \pi_U$ ) for  $\pi$  is then calculated (Clopper - Pearson method with mid-p correction) based on the number of participants with a conversion in one of the treatment groups (for example H4:IC31), relative to the total number of participants  $n = n_A + n_B$  who had at a conversion in either of the two compared treatment groups. The following SAS® code will be used:

```
PROC FREQ DATA = <>;

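### One exploratory end-of-study row counts Month 6/12 converters as reverted only if the call-back test is negative, although its own label accepts a missing result

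*SAP*

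**What the plan says.** The table on trends in sustained conversions and end-of-study reversions (SAP 14.3.2) has a row for participants "who never converted or converted with reversion and have non-positive (i.e., negative or missing) end of study QFT-GIT values". SAP 14.3.3 repeats the label: "Prevention of conversion OR conversion with reversion and non-positive (i.e., negative or missing) QFT-GIT results at the end of the study". In both places, non-positive covers a negative and a missing result.

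The derivation under that label has separate clauses by time of conversion:

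- Month 18/24 converters: "Participants who initially converted at Month 18 or Month 24 (i.e., +/-/-, +/+/-, +/m/-, +/-/m) and later reverted OR". A missing last test after a negative (+/-/m) counts.
- Month 6/12 converters: "Participants who initially converted at Month 6 or Month 12 and have a call-back Month 24 visit that is negative". Eight four-position patterns follow (conversion, 3 months, 6 months, call-back), and all end in a negative.

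The companion six-month category in the same section counts "Participants who have a negative QFT-GIT value at the last available testing timepoint within six months after their initial conversion", and its list includes +/-/m.

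The denominator of the end-of-study row (SAP 14.3.2) removes only +/m/m, +/+/m/m (printed with a slash missing) and +/m/m/m. The row gets a Pearson chi-square test and a vaccine efficacy (VE) estimate with a 95% CI.

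The call-back applies to Month 6/12 converters, at least 24 months after first vaccination. Participants were approached for it (SAP 3.1), and Protocol 3.2.1 requires separate agreement: "Informed consent will be obtained by the use of a written supplemental consent form".

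**The concern.** The label and the Month 6/12 clause give different answers for an early converter who has a recorded negative and then does not attend the call-back. The label makes this participant a success. The clause does not, and the denominator rule does not set the participant aside, so by default the result is a failure. The treatment is uneven: +/+/m/m, with no evidence of reversion, is removed as unclassifiable, while +/-/m/m, with a documented reversion, is kept as a failure.

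Only participants who reverted can be misplaced in this way, so an arm with more reversion loses more of its successes. The protocol (2.2 and 7.3) names initial infection followed by clearance as a possible mechanism of action. In this row the rule therefore works against the effect the row is meant to show.

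Some missing call-backs are foreseeable. The visit needs supplemental consent and falls about 12 months after a Month 6 converter's last scheduled visit (Month 12) and about 6 months after a Month 12 converter's (Month 18).

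**Working it through.** **Step 1: patterns.** The SAP states no figure for this row, so there is none to reproduce. With three results after conversion, each +, - or m, a Month 6/12 converter has 3 × 3 × 3 = 27 possible patterns. Nine end in a negative call-back. Eight of these are listed; +/m/+/- is omitted although its call-back is negative. Nine end in a missing call-back:

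| Pattern | Any negative | Last available result | In denominator | Counted as success |
|---|---|---|---|---|
| +/-/-/m | yes | - | yes | no |
| +/+/-/m | yes | - | yes | no |
| +/m/-/m | yes | - | yes | no |
| +/-/m/m | yes | - | yes | no |
| +/-/+/m | yes | + | yes | no |
| +/+/+/m | no | + | yes | no |
| +/m/+/m | no | + | yes | no |
| +/+/m/m | no | + | no | no |
| +/m/m/m | no | + | no | no |

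The first four conflict both with the label and with the last-available-result rule of the six-month category. The fifth fits the literal label (a reversion, then a missing result), but its last result is positive.

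**Step 2: effect on the apparent reduction.** Inputs from Protocol 7.6: placebo reversion 20%, and persistent conversion halved solely through reversion. The persistent shares of converters are then 1 − 0.20 = 0.80 and 0.80 × 0.5 = 0.40, so vaccine reversion is 60%. Assumptions: equal conversion in both arms, no reconversion, and a share m of call-backs missing at random (10%, 20%, 30%). I take VE to be calculated on failures, since the row itself is a favourable outcome.

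Share of converters converting at Month 6 or 12, with hazard 10% and loss 7% per year (Protocol 7.6), from Day 84 to Day 336 out of Day 84 to Day 672:

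(1 − exp(−0.17 × 252/365.25)) / (1 − exp(−0.17 × 588/365.25)) = 0.1107/0.2394 = 0.46.

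Share of converters failing the row = (1 − r) + r × 0.46 × m, where r is the reversion rate:

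| m (assumed) | Placebo, r = 0.20 | Vaccine, r = 0.60 | Ratio | Apparent reduction |
|---|---|---|---|---|
| 0 | 0.800 | 0.400 | 0.500 | 50% |
| 0.10 | 0.809 | 0.428 | 0.528 | 47% |
| 0.20 | 0.818 | 0.455 | 0.556 | 44% |
| 0.30 | 0.828 | 0.483 | 0.583 | 42% |

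Never-converters are successes in both arms. With equal conversion and equal denominators, the ratio over converters is therefore also the ratio for the row.

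**Step 3: number of participants.** Month 6/12 converters per arm of 330 at 10% per year, ignoring loss: 330 × (1 − exp(−0.10 × 252/365.25)) = 22.0.

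- At 20% reversion: 22.0 × 0.20 × 0.10 = 0.4 to 22.0 × 0.20 × 0.30 = 1.3 misplaced.
- At 60% reversion: 22.0 × 0.60 × 0.10 = 1.3 to 22.0 × 0.60 × 0.30 = 4.0.
- At 17% conversion per year (the site average in Protocol 7.6) there are 36.5 converters. With an assumed 40% reversion and 50% missing, 36.5 × 0.40 × 0.50 = 7.3.

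**The case against.** The strongest reply is that this is one row of one exploratory table, and the same participants appear as reverters elsewhere. They count in the converted-with-reversion row of the same table, in the six-month row when their last available result is negative, in the first-reversion table and the Kaplan-Meier plot of time to first reversion, and in the converted/reverted table. The pattern listing will show each of them. SAP 14.3.1 also warns that analyses of post-randomization subsets with differential follow-up may be biased, and allows supportive analyses. All of this stands, and it limits what is at stake.

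Two further points stand. The missed-call-back share is an assumption: SAP 3.1 records that the DMC recommended a 24-month test for all participants, including converters, so attendance may be good. And 50% is the known true value only if no reverter reconverts. The SAP plans a listing of participants who converted, reverted and converted again, so carrying an early negative forward can err in the other direction.

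It might also be said that only the call-back is a valid end-of-study test. That does not rescue the text: the label would then be wrong to accept a missing result, and keeping these participants in the denominator as failures would still be unexplained.

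A reader might infer that the SAP contradicts itself by making one participant both not reverted and not sustained. It does not. It never assigns a not-reverted status, and +/-/+/+ fails this row and is also No for end-of-study sustained conversion by design. The contradiction is between the row's label and its pattern list.

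**Conclusion.** The Month 6/12 clause in SAP 14.3.3 does not implement the category it sits under, and it departs from the Month 18/24 and six-month rules beside it. Programmed as written, it scores documented reverters without a call-back as failures and dilutes this row's VE if a vaccine increases reversion. Under the protocol's scenario with 10% to 30% of call-backs missing, the apparent reduction over all converters is about 47% to 42% instead of 50%. That rests on assumed attendance, missingness at random, no reconversion, a 46% early-converter share and a large vaccine effect on reversion. The counts are small, about 0.4 to 1.3 per arm at 20% reversion and 10% annual conversion. With few converters, a few participants can still move the estimate.

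A reader might infer a larger loss by looking at Month 6/12 converters alone. There the shares are 82% vs 46%, 84% vs 52% and 86% vs 58%, and the reduction falls to 44%, 38% and 33%. The row does not report that subset. Nor do the documents support any effect on the primary or secondary endpoint, which do not use this derivation.

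**What to change.** Before unblinding for the final analysis, amend SAP 14.3.2 and 14.3.3 as follows:

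- Add +/-/-/m, +/+/-/m, +/m/-/m and +/-/m/m to the Month 6/12 list, under the six-month category's rule that the last available result is negative.
- State how +/-/+/m is classed. The literal label makes it a success; the last-available-result rule makes it a failure.
- Add +/m/+/-, whose call-back is negative.
- Correct the exclusion printed as +/+m/m to +/+/m/m.

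Dropping all Month 6/12 converters without a call-back should not be the main rule. It selects on post-randomization attendance, removes converters while keeping never-converters, and also removes failures such as +/+/+/m.

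The cost is SAP wording and one derivation, with no new data; the denominator rule is otherwise unchanged. The downside is that, for these participants, end-of-study status rests on a result from up to about 6 months after conversion, so a later reconversion would be missed. A footnote giving the number so classified in each arm would make this visible.

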  - o For the sensitivity analysis the following SAS code will be implemented:

```
PROC LIFETEST DATA = <> METHOD=lt INTERVALS=(0 to 2 by 0.5)
PLOTS=(s) ;
TIME Years*Censored(1) ;
FREQ count;
RUN;
```

- Vaccine efficacy is derived as:
  - o  $VE = 1 - \text{Hazard Rate Ratio (Vaccine/comparator)}$
  - o The hazard ratio is estimated based on the following Cox regression model:

```
PROC PHREG DATA = <>;
MODEL Time to Event (Months) * Censor (1) = Treatment Group;
RUN;
```

- Censor = 1 represents censored participant.
    - Censor = 0 represents participant who experienced an event.
    - Months represent the available follow-up time (months) per participant since randomization.
  - o The 80% CI is based on the two-sided hazard ratio confidence interval and will be derived as:
    - $VE_{\text{lower limit}} = 1 - \text{Hazard ratio}_{\text{upper limit}}$
    - $VE_{\text{upper limit}} = 1 - \text{Hazard ratio}_{\text{lower limit}}$
  - o The 95% CI is based on the two-sided hazard ratio confidence interval.

- For the sensitivity analysis, interval censoring will be used based on the following code:

```
PROC ICPHREG DATA = <>;
MODEL (left, right) = Treatment Group /b=pch(NINTERVAL=X);
RUN;
```

- Left represents left censoring value in months.
  - Right represents right censoring value in months.
  - Left and right censoring values are dependent on where the event is identified:

Visit at Which Primary Event Identified	Left Censoring Value	Right Censoring Value
M6	3	6
M12	6	12
M18	12	18
M24	18	24

Document: Aeras\_C-040-404\_SAP\_V2\_0

Author: [name]

Version Number:

2.0

Version Date:

29SEP2017

Template No: CS\_TP\_BS016 – Revision 3

Reference: CS\_WI\_BS005

Effective Date: 01May2012

Copyright © 2012 Quintiles Transnational Corp. All rights reserved.

The contents of this document are confidential and proprietary to Quintiles Transnational Corp. Unauthorized use, disclosure or reproduction is strictly prohibited.

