### 14.3.2. ANALYSIS OF EXPLORATORY EFFICACY ENDPOINT

The following tables will be presented for the Modified Intent-to-treat analysis set:

- QuantiFERON levels (IU/mL) upon and following first positive QFT-GIT result:
  - o Default summary statistics for QFT-GIT results at the following time points:
    - First positive QFT-GIT result:
      - The p-value based on the Mann-Whitney-Wilcoxon test will be used for pair-wise comparisons between treatment groups.
    - 3 months-post first positive QFT-GIT result:
      - Number and percentage (%) of participants with a negative QFT-GIT.
    - 6 months-post first positive QFT-GIT result:
      - Number and percentage (%) of participants with a negative QFT-GIT.
  - o This table is to include all participants with at least one positive post-Day 84 QFT-GIT result.
  - o This table will be repeated for the Per Protocol analysis set.
- First QuantiFERON reversion:
  - o Number of participants with first QFT-GIT negative value within the following categories will be included:
    - Within 3 months post-conversion.
    - Within 6 months post-conversion.
    - At any time during follow-up.
  - o At risk defined as participants with:
    - A primary endpoint.
    - A QFT-GIT result available at the relevant visit within 6 months (for the first two lines) or at any time post-initial conversion (for the third line) after the primary endpoint occurrence.
  - o This table will be repeated for the Per Protocol analysis set.
- Alternative QFT-GIT thresholds:
  - o Number and percentage of participants who EVER experienced the following alternative threshold values (i.e., at any post-Day 84 timepoint):
    - $\geq 0.20$ .
    - $< 0.2$  at any time point prior to conversion and  $> 0.70$  at any time point post-Day 84.
    - $> 0.70$ .
    - $> 4.0$ .
  - o Vaccine efficacy presented:
    - Point estimate (based on the conditional binomial distribution).
    - 95% CI (based on the conditional binomial Clopper-Pearson method with mid-p correction).
  - o This table will be repeated for the Per Protocol analysis set.
- Trends in QFT-GIT sustained conversions and end-of-study reversions:
  - o Number and percentage (%) of participants in each category:
    - Participants who were negative at Month 24 or the Month 24 call-back visit. Percentages (%) will be calculated based on the number of participants with non-missing Month 24 or Month 24 call-back values.

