    TABLE Events / BINOMIAL (midp P=0.05);
RUN;
```

Based on the exact 95% CI for  $\pi$ , an exact 95% CI ( $\theta_L, \theta_U$ ), for the rate ratio  $\theta$  is then calculated by solving the equations:

$$\frac{\theta_L F_A}{\theta_L F_A + F_B} = \pi_L$$

$$\frac{\theta_U F_A}{\theta_U F_A + F_B} = \pi_U$$

Solving  $\theta_L$  and  $\theta_U$  yields:

$$\theta_L = \left( \frac{\pi_L}{1 - \pi_L} \right) \left( \frac{F_B}{F_A} \right)$$

$$\theta_U = \left( \frac{\pi_U}{1 - \pi_U} \right) \left( \frac{F_B}{F_A} \right)$$

Finally, the exact 95% CI ( $VE_L, VE_U$ ) for VE is calculated as

$$VE_L = (1 - \theta_U)$$

$$VE_U = (1 - \theta_L)$$

In summary, the VE point estimate and confidence limits for the aforementioned binomial proportion ( $\pi$ ) will be substituted in the following formula in order to obtain the corresponding confidence limits for the VE:

$$VE = \left( \frac{(\pi) F_B}{(1 - \pi) F_A} \right)$$

Document: Aeras\_C-040-404\_SAP\_V2\_0

Author: [name]

Version Number:

2.0

Version Date:

29SEP2017

Template No: CS\_TP\_BS016 – Revision 3

Reference: CS\_WI\_BS005

Effective Date: 01May2012

Copyright © 2012 Quintiles Transnational Corp. All rights reserved.

The contents of this document are confidential and proprietary to Quintiles Transnational Corp. Unauthorized use, disclosure or reproduction is strictly prohibited.

Where the lower confidence limit for VE is obtained by substituting the upper confidence limit for  $\pi$  in the above formulae, and the upper confidence limit for VE is obtained by substituting the lower confidence limit for  $\pi$  in the above formula.

- Bacteriologically confirmed TB:
  - o Positive culture result (Mycobacterium tuberculosis positive)  
OR
  - o Positive GeneXpert result (MTB detected) (with or without clinical symptoms and/or positive chest x-ray).

---

Document: Aeras\_C-040-404\_SAP\_V2\_0

Author: [name]

Version Number:

2.0

Version Date:

29SEP2017

Template No: CS\_TP\_BS016 – Revision 3

Reference: CS\_WI\_BS005

Effective Date: 01May2012

Copyright © 2012 Quintiles Transnational Corp. All rights reserved.

The contents of this document are confidential and proprietary to Quintiles Transnational Corp. Unauthorized use, disclosure or reproduction is strictly prohibited.

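### As printed, the summary formula for conditional-binomial vaccine efficacy in SAP 14.3.3 lacks the leading 1 − and gives the rate ratio; check the source page and restore it if absent

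*SAP*

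**What the plan says.** SAP 14.3.3 treats the conversion counts in two groups as independent Poisson variables and conditions on their total, so that n_A is binomial with probability π = θF_A/(θF_A + F_B). F_A and F_B are the total follow-up times. In the SAP's example A is H4:IC31 and B is Placebo, so θ is the vaccine-to-comparator rate ratio.

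The section solves for θ_L and θ_U and sets VE_L = 1 − θ_U and VE_U = 1 − θ_L. It then closes with a sentence that begins "In summary, the VE point estimate and confidence limits for the aforementioned binomial proportion" and directs that these be substituted in VE = π·F_B / ((1 − π)·F_A). The sentence after the formula begins "Where the lower confidence limit for VE is obtained by substituting the upper confidence limit for" π, and gives the mirror rule for the upper limit.

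Section 14.3.2 uses this method in two exploratory tables. For the alternative thresholds, the VE entries begin "Point estimate (based on the conditional binomial distribution" and "95% CI (based on the conditional binomial Clopper-Pearson method with mid-p correction". The table of trends in sustained conversions and end-of-study reversions uses the same conditional-binomial method for both the estimate and the interval. Elsewhere (14.1.3 and 14.2.3), VE is 1 minus a hazard ratio.

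**The concern.** The formula labelled VE has the same form as the expression that the section has just solved for θ. A programmer or validator who takes the closing sentence as the specification would report the rate ratio under the label of vaccine efficacy. The two correct lines above it cover only the limits, so the closing formula is the only one in 14.3.3 for the conditional-binomial point estimate.

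At stake is the reading of the alternative-threshold analysis, which is a stated exploratory objective, and of the trends table. An estimate of θ in place of 1 − θ understates a strong effect, overstates a weak one, and could fall outside an interval computed from the correct lines.

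**Working it through.** **Inputs.** The definition of π, the solutions for θ_L and θ_U, the two VE-limit lines, the closing formula and the substitution rule are all from SAP 14.3.3. The 64 target endpoints and the 50% design reduction are from Protocol 2.2 and 7.6. The arm-level counts below are assumptions, since the documents give none: 64 shared evenly over three arms is about 21 each, and 32 + 16 + 16 = 64 corresponds to a 50% reduction in both vaccine arms with equal follow-up.

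**Step 1: reproduce the SAP's solution.** From π = θF_A/(θF_A + F_B):

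- π(θF_A + F_B) = θF_A
- πF_B = θF_A(1 − π)
- θ = [π/(1 − π)]·(F_B/F_A)

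This agrees with the SAP's θ_L and θ_U.

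**Step 2: compare the closing formula.** π·F_B / ((1 − π)·F_A) is the right-hand side of Step 1, that is, θ. The value consistent with VE_L = 1 − θ_U and VE_U = 1 − θ_L is 1 − θ.

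**Step 3: the substitution rule.** θ increases with π, so 1 − θ decreases with π. Taking the lower VE limit from the upper limit of π is right for 1 − θ. Applied to the printed formula, the same rule returns the larger value as the lower limit.

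**Step 4: numbers.** Mid-p 95% limits for π solve P(X > x) + ½P(X = x) = 0.025 (lower) and P(X < x) + ½P(X = x) = 0.025 (upper). Equal follow-up is assumed, so F_B/F_A = 1.

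- 21 v 21: π = 0.5 (0.3513 to 0.6487), θ = 1.0000 (0.5416 to 1.8462).
- 16 v 32: π = 0.3333 (0.2114 to 0.4749), θ = 0.5000 (0.2680 to 0.9043).

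| Events, vaccine v placebo | VE, formula as printed | Printed 'lower', 'upper' | VE = 1 − θ | Limits from 1 − θ |
|---|---|---|---|---|
| 21 v 21 | 100.0% | 184.6%, 54.2% | 0.0% | −84.6% to 45.8% |
| 16 v 32 | 50.0% | 90.4%, 26.8% | 50.0% | 9.6% to 73.2% |
| 32 v 16 | 200.0% | 373.1%, 110.6% | −100.0% | −273.1% to −10.6% |
| 0 v 32 | 0.0% | 9.8%, 0.0% | 100.0% | 90.2% to 100.0% |

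In the first row, a point estimate from the printed formula (100%) lies outside the interval from the VE_L and VE_U lines. In the second row the two point estimates coincide, because θ = 1 − θ at θ = 0.5. A program check at the design effect would therefore not detect the error in the point estimate.

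**The case against.** Four points can be made on the other side.

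First, the 1 − may be present on the page and lost when the PDF was read. Just before, the definition of θ appears without the division sign that the formula for π requires; that is most likely a reading loss and is not counted here as an error. The outer brackets around the closing formula serve no purpose as printed but would be natural after 1 −. Against this, 1 − survives in both θ solutions, in both VE-limit lines and in the denominator of this formula. The possibility stands, which is why the remedy starts with the source page.

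Second, the context corrects the slip. The limits are properly defined immediately above, the substitution rule makes sense only for 1 − θ, and VE is 1 minus a ratio elsewhere in the SAP. This stands for the limits. It does not supply a correct formula for the point estimate.

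Third, a reader might infer that the reversed limits are a second defect. They are not: the substitution rule is correct, and the reversal follows from the same missing 1 −.

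Fourth, a reader might infer that the trial would report an ineffective vaccine as 100% efficacious. The documents do not support that. They contain no program or output, the correct limit lines may well have been followed, and literal coding would give VE limits above 100% in reverse order at the null, which is conspicuous. Nor does the point reach the main results: primary VE, secondary VE (including its alternative-threshold version) and end-of-study sustained-conversion VE all use 1 minus the Cox hazard ratio.

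**Conclusion.** As printed, the closing formula in SAP 14.3.3 equals the rate ratio and contradicts the lines on either side of it. The algebra holds for any counts and any follow-up. The consequence is conditional: if the formula is coded literally, the conditional-binomial point estimates in two exploratory tables could be θ instead of 1 − θ, an error that is zero at a rate ratio of 0.5 and reaches 100 percentage points at no effect. The event counts and equal follow-up in the illustration are assumptions. This is probably a typographical omission in the SAP or a loss in reading the PDF. It deserves correction because it is the only formula given for that estimate, but it bears on no primary or secondary conclusion.

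**What to change.** Check the source page of SAP 14.3.3. If the 1 − is there, the point is closed. If it is absent:

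- write VE = 1 − [π/(1 − π)]·(F_B/F_A) for the point estimate and the limits;
- leave the substitution rule as it stands, since it then agrees with VE_L = 1 − θ_U and VE_U = 1 − θ_L;
- validate the program for the two exploratory tables at a rate ratio other than 0.5, for example equal counts with equal follow-up, which must return 0%.

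The cost is one line of SAP text and one test case. No data collection, analysis set or other analysis changes.
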